5. STUDY CONDUCT

5.1 Restrictions during the study

- Healthy volunteers will be fasted from 10 hours prior to the IP administration through 4 hours after administration. No fluids will be allowed from 1 hour prior to IP administration until 1 hour after IP administration, except the water needed (240 mL) to consume the IP. Thereafter, healthy volunteers will be allowed to have free access to water (see Section 5.5.2).
- The volunteer must be semi-supine (minimum of 30 degrees) for 4 hours following each IP administration unless specified for certain assessments eg, ECG.
- The healthy volunteers will be fasted for 4 hours prior to any clinical laboratory evaluations.
- Volunteers will be asked to abstain from grapefruit or grapefruit juice, Seville oranges, quinine (eg, tonic water) within 7 days prior to admission on Day -1.
- Volunteers will be asked to abstain from alcohol for 72 hours before admission on Day -1.
- During residency, volunteers will receive a standard high fibre diet and should abstain from consuming alcohol, high energy drinks (e.g. Red Bull), grapefruit-containing products, food containing poppy seeds, and any over the counter medication or herbal preparations until after their final follow-up visit on Day 7 has been completed. Volunteers should also limit their caffeine intake to equivalent of 3 cups of coffee per day (1 cup =12 oz soda, 6 oz coffee, or 8 oz tea). No additional food or beverages must be consumed whilst in the study centre.
- Volunteers will be required to abstain from blood or plasma donation until 3 months after the final medical examination on Day 7.
- If a volunteer does not comply with these restrictions or test positive to any laboratory tests (eg, drugs of abuse and/or alcohol) they may be excluded or withdrawn from the study.
- Male volunteers with sexual partners who are pregnant or who could become pregnant (ie, women of child-bearing potential) should use barrier methods of contraception for

at least 14 days after completing the study to avoid pregnancy and/or potential adverse effects on the developing embryo. Volunteers should avoid sperm donation during and for 14 days after study completion. Reliable methods of contraception should be used consistently and correctly.

Acceptable methods for volunteers' partners include:

- Implants, injectables, combined oral contraceptives (which must all be combined with barrier methods of contraception), some intrauterine devices, vasectomised partner (which must all be combined with barrier methods of contraception), and sexual abstinence.

Acceptable methods for volunteers include:

- Volunteers will be required to use reliable methods of contraception (condom and spermicide) for the duration of the study until 14 days after the IP administration.
- Volunteers should not take vitamin E supplements or multivitamin supplements. Throughout the study, healthy volunteers should avoid the addition of any concomitant medications, in particular any that are likely to affect the metabolism of selumetinib (eg, CYP1A2 or 3A4 inhibitors or inducers), unless considered clinically essential for management of concurrent conditions as judged by the Investigator.
- Volunteers should avoid excessive sun exposure and use adequate sunscreen protection, if sun exposure is anticipated. Volunteers should use sunscreen for up to 14 days after the administration of [¹⁴C]-selumetinib.
- Volunteers will be required to avoid excessive exercise during the study.

5.2 Subject enrolment and initiation of investigational product

The Principal Investigator will:

1. Obtain signed informed consent from the potential volunteer before any study specific procedures are performed.
2. Assign potential volunteer a unique enrolment number, beginning with 'E#'.
3. Determine volunteer eligibility. See Sections 4.1 and 4.2.

If a volunteer withdraws from participation in the study, then his enrolment code cannot be reused. Enrolment codes will be assigned strictly sequentially as volunteers become eligible for enrolment.

5.3 Procedures for handling subjects incorrectly enrolled or initiated on investigational product

Volunteers who fail to meet the inclusion/exclusion criteria should not, under any circumstances, be enrolled or receive the IP. There can be no exceptions to this rule.

Where volunteers that do not meet the inclusion and/or exclusion criteria, are enrolled in error, or incorrectly started on treatment, or where volunteers subsequently fail to meet the study criteria post initiation, the Investigator should inform the AstraZeneca Clinical Pharmacology Alliance (CPA) physician immediately.

The AstraZeneca CPA physician is to ensure all such contacts are appropriately documented.

5.4 Blinding and procedures for unblinding the study (Not applicable)

5.5 Treatments

5.5.1 Identity of investigational product(s)

Table 4 Formulation of Investigational Product

Investigational product	Dosage form and strength	Manufacturer
Selumetinib	Oral capsules 25 mg (free base equivalent) selumetinib Hyd Sulfate capsule containing 7.52 MBq (203.3 µCi) [¹⁴ C]-selumetinib	

5.5.2 Doses and treatment regimens

Each healthy volunteer will receive 3 x 25 mg [¹⁴C]-selumetinib Hyd-Sulfate oral capsules (FBE) as a single dose on Day 1. Healthy volunteers should be fasted from 10 hours prior to IP administration and remain fasted for 4 hours after administration. No fluids will be allowed from 1 hour prior to IP administration until 1 hour after IP administration, except the water needed (240 mL) to consume the IP. Thereafter, healthy volunteers will be allowed to have free access to water.

5.5.3 Labelling

Labels will be prepared in accordance with Good Manufacturing Practice (GMP) and local regulatory guidelines. The labels will fulfil GMP Annex 13 requirements for labelling.

5.5.4 Storage

Selumetinib capsules are supplied in 50 mL DUMA high density polypropylene (HDPE) bottles with DUMA polypropylene cap and integral desiccant.

The IP should be kept in a secure place under appropriate storage conditions. The IP label on the bottle specifies the appropriate storage.

5.6 Concomitant and post-study treatment(s)

Use of concomitant medications, herbal supplements, and/or ingestion of foods that significantly modulate CYP3A4 and/or CYP1A2 activity or which are significantly metabolised by CYP3A4 and/or CYP1A2 should be avoided. Any prescribed or non prescribed medication including drugs with hepatic enzyme-altering properties, such as St

John's wort, antacids, analgesics, herbal remedies, vitamins, and minerals should be avoided for 3 weeks (or longer depending on the medication's half-life) before administration of the IP until after the final follow-up visit (see Section 4.2).

Healthy volunteers should abstain from using any medication, over-the-counter remedies, herbal medications, high-dose or "mega" vitamins, or medicines purchased via the Internet from 3 weeks before dosing until after follow-up. Use of 1 g paracetamol 6 hourly (to a maximum daily dose of 4 g) is permitted, however the Investigator should be informed so it can be recorded.

Other medication, which is considered necessary for the healthy volunteer's safety and well being, may be given at the discretion of the Investigator and recorded in the appropriate sections of the paper Case Report Form (CRF).

5.7 Treatment compliance

The date and time of administration of all study drugs (including IPs) should be recorded in the appropriate sections of the CRF.

5.7.1 Accountability

The IP provided for this study will be used only as directed in the study protocol. The IP will be administered under supervision.

5.8 Discontinuation of investigational product (Not applicable)

5.9 Withdrawal from study

Healthy volunteers are at any time free to withdraw from study (IP and assessments), without prejudice to further treatment (withdrawal of consent). These healthy volunteers will always be asked about the reason(s) and the presence of any AEs. If possible, they will be seen and assessed by an Investigator. Adverse events will be followed up (See Sections 6.4.3 and 6.4.4).

Withdrawn healthy volunteers will not be replaced.

6. COLLECTION OF STUDY VARIABLES

It is important that PK sampling occurs as close as possible to the scheduled time (see Table 2 and Table 3). In order to achieve this, other assessments scheduled at the same time may be initiated prior to the time point. The sequence at a particular time point is:

1. 12-lead ECG.
2. Blood pressure and pulse rate (and body temperature).
3. Pharmacokinetic blood sample.

4. Safety laboratory assessment blood sample.
5. Pharmacokinetic urine sample.

Pre-dose assessments may be performed up to 60 minutes prior to IP administration.

For occasions when more than 1 assessment is required at a particular time point, PK blood samples should be prioritised.

6.1 Recording of data

The Investigator will ensure that data are recorded on the paper CRF as specified in the study protocol and in accordance with the instructions provided.

The Investigator ensures the accuracy, completeness, legibility, and timeliness of the data recorded and of the provision of answers to data queries according to the Clinical Study Agreement (CSA). The Investigator will sign the completed paper CRF. A copy of the completed paper CRF will be archived at the study centre.

6.2 Data collection at enrolment and follow-up

Following a signed informed consent, healthy volunteers will be screened for eligibility to be enrolled in the study.

6.2.1 Enrolment procedures

At enrolment each potential volunteer will provide written informed consent prior to starting any study-specific procedures.

Demographic data and other characteristics will be recorded and will include date of birth, gender, race, ethnicity, alcohol consumption, and smoking history.

Each volunteer will undergo screening during the 28 days prior to Day -1 to confirm eligibility. This will consist of:

- Review of inclusion and exclusion criteria
- A standard medical, surgical, and smoking history of the volunteer inclusive of prior and concomitant medications
- A complete physical examination
- Eye examination
- Height and weight measurements and calculation of BMI
- Vital sign measurements (supine pulse rate and blood pressure)
- Recording of 12-lead ECG
- Echocardiogram

- Collection of blood sample for predose safety laboratory assessments (clinical chemistry and haematology), and screening for hepatitis B virus surface antigen, antibodies to hepatitis C virus, and HIV.
- Collection of urine sample for routine urinalysis and urine microscopy (if there is an abnormal urinalysis result), drugs of abuse, alcohol, and cotinine
- Serious adverse event (SAE) recording

6.2.2 Follow-up procedures

The final medical assessment on Day 7 or on the last day of urine/faecal collection (whichever is later) will include the assessment of concomitant medication, complete physical examination, clinical chemistry, haematology, PK blood collection, urinalysis, faeces collection, supine blood pressure and pulse rate, weight and record AEs/SAEs.

6.3 Efficacy (Not applicable)

6.4 Safety

The Principal Investigator is responsible for ensuring that all staff involved in the study is familiar with the content of this section.

6.4.1 Definition of adverse events

An AE is the development of an undesirable medical condition or the deterioration of a pre-existing medical condition following or during exposure to a pharmaceutical product, whether or not considered causally related to the product. An undesirable medical condition can be symptoms (eg, nausea, chest pain), signs (eg, tachycardia, enlarged liver) or the abnormal results of an investigation (eg, laboratory findings, ECG). In clinical studies, an AE can include an undesirable medical condition occurring at any time, including run-in or washout periods, even if no IP has been administered.

The term AE is used to include both serious and non-serious AEs.

6.4.2 Definitions of serious adverse event

An SAE is an AE occurring during any study phase (ie, screening, treatment, residency, and follow-up [Day 7]), that fulfils one or more of the following criteria:

- Results in death
- Is immediately life-threatening
- Requires in-patient hospitalisation or prolongation of existing hospitalisation
- Results in persistent or significant disability/incapacity or substantial disruption of the ability to conduct normal life functions
- Is a congenital abnormality or birth defect

- Is an important medical event that may jeopardise the healthy volunteer or may require medical intervention to prevent one of the outcomes listed above

For further guidance on the definition of an SAE, see [Appendix B](#) to the CSP.

6.4.3 Recording of adverse events

Time period for collection of adverse events

Adverse events will be collected from informed consent up to Day 7 or the last day of urine/faecal collection (whichever is later). Serious AEs will be recorded from the time of informed consent.

Follow-up of unresolved adverse events

Any AEs that are unresolved on Day 7 or the last day of urine/faecal collection (whichever is later), are to be followed up by the Investigator. A follow-up phone call can be conducted 5 to 10 days following discharge on Day 7 or the last day of PK blood sample collection (whichever is later), to monitor unresolved AEs. Adverse events will not be monitored following the follow-up phone call.

AstraZeneca retains the right to request additional information for any healthy volunteer with ongoing AE(s)/SAE(s) at the end of the study, if judged necessary.

Variables

The following variables will be collected for each AE;

- AE (verbatim)
- The date and time when the AE started and stopped
- Maximum intensity
- Whether the AE is serious or not
- Investigator causality rating against the IP (yes or no)
- Action taken with regard to IP
- AE caused healthy volunteer's withdrawal from study (yes or no)
- Outcome

In addition, the following variables will be collected for SAEs:

- Date AE met criteria for serious AE
- Date Investigator became aware of serious AE

- AE is serious due to
- Date of hospitalisation
- Date of discharge
- Probable cause of death
- Date of death
- Autopsy performed
- Causality assessment in relation to study procedure(s)
- Causality assessment in relation to other medication
- Description of AE

The following intensity ratings will be used:

1. Mild (awareness of sign or symptom, but easily tolerated)
2. Moderate (discomfort sufficient to cause interference with normal activities)
3. Severe (incapacitating, with inability to perform normal activities)

It is important to distinguish between serious and severe AEs.

Severity is a measure of intensity whereas seriousness is defined by the criteria in Section [6.4.2](#).

An AE of severe intensity need not necessarily be considered serious. For example, nausea that persists for several hours may be considered severe nausea, but not an SAE. On the other hand, a stroke that results in only a limited degree of disability may be considered a mild stroke but would be an SAE.

Causality collection

The Investigator will assess causal relationship between IP and each AE, and answer “yes” or “no” to the question “Do you consider that there is a reasonable possibility that the event may have been caused by the IP?”

For SAEs causal relationship will also be assessed for other medication and study procedures. Note that for SAEs that could be associated with any study procedure the causal relationship is implied as “yes”.

A guide to the interpretation of the causality question is found in [Appendix B](#) to the CSP.

Adverse Events based on signs and symptoms

All AEs spontaneously reported by the healthy volunteer or reported in response to the open question from the study personnel: “Have you had any health problems since you were last asked?”, or revealed by observation will be collected and recorded in the CRF. When collecting AEs the recording of diagnoses is preferred (when possible) to recording a list of signs and symptoms. However, if a diagnosis is known and there are other signs or symptoms that are not generally part of the diagnosis, the diagnosis and each sign or symptom will be recorded separately.

Adverse Events based on examinations and tests

The results from protocol mandated laboratory tests and vital signs will be summarised in the Clinical Study Report (CSR). Deterioration as compared to baseline in protocol-mandated laboratory values, vital signs, ECGs, and other safety assessments should therefore only be reported as AEs if they fulfil any of the SAE criteria.

If deterioration in a laboratory value or vital sign is associated with clinical signs and symptoms, the sign or symptom will be reported as an AE and the associated laboratory result or vital sign will be considered as additional information. Wherever possible the reporting Investigator uses the clinical, rather than the laboratory term (eg, anaemia versus low haemoglobin value). In the absence of clinical signs or symptoms, clinically relevant deteriorations in non-mandated parameters should be reported as AE(s).

Any new or aggravated clinically relevant abnormal medical finding at a physical examination as compared with the baseline assessment will be reported as an AE.

NB. Cases where a healthy volunteer shows an AST or ALT ≥ 3 x upper limits of normal (ULN) or total bilirubin ≥ 2 x ULN may need to be reported as SAEs, please refer to [Appendix D](#) ‘Actions required in cases of combined increase of Aminotransferase and Total Bilirubin – Hy’s Law’, for further instructions.

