- ^e Creatinine clearance will be calculated at screening using the Cockcroft-Gault formula.
- ^f Urine samples will be collected along with the other clinical laboratory evaluations. Urinalysis to be performed by standard dipstick analysis. Microscopy should only be performed if the urinalysis shows a positive result.
- ^g Alcohol will be assessed by an alcohol breath test. Smoking will be assessed by performing a breath carbon monoxide test. A positive test will constitute a value of greater than 10 ppm.
- ^h Supine blood pressure and pulse rate will be measured after the healthy volunteer has rested in a supine position for at least 10 minutes prior to the evaluation. If possible, the same arm and equipment should be used for each evaluation (refer to [Table 3](#) for time points).
- ⁱ Height and weight will be evaluated at screening. Only weight will be evaluated at Day -1 and on Day 7. The healthy volunteers will be required to remove their shoes and wear light indoor clothing for these measurements.
- ^j Eligible healthy volunteers will receive a single administration of IP on Day 1.
- ^k Blood, plasma, urine, and faeces samples will be collected as per [Table 3](#) for time points.
- ^l Only SAEs will be collected from the time the ICF is signed. AEs will be collected from Day 1 after the IP administration. For unresolved AEs/SAEs a follow-up phone call can be conducted 5 to 10 days following discharge to monitor unresolved AEs/SAEs. Unresolved AEs/SAEs will not be monitored following the follow-up phone call.
- ^m Electrocardiograms will be recorded in the supine position after the healthy volunteer has rested in this position for at least 10 minutes.
- ⁿ Echocardiogram (as early as 28 days prior to administration of the IP) will be conducted at screening (will be considered the baseline value; no need to repeat) and for cause (on occurrence of cardiac events only).
- ^o Ophthalmic examination (best corrected visual acuity, intraocular pressure, slit-lamp fundoscopy) will be conducted at screening (will be considered the baseline value; no need to repeat) and for cause (on occurrence of AE only).

Table 3 Detailed Study Plan during residential period

t (hours)	PK Blood Collection ^a	[¹⁴ C] Whole Blood ^b	[¹⁴ C] plasma ^c	Urine Collection (20 mL aliquot) ^{d, f}	Faeces Collection ^{d, f}	Supine Blood Pressure	Blood sampling for metabolite ID ^e	
0	X	X	X	X		X	X	
0.5	X	X	X	X	X			
1	X	X	X					
1.5	X	X	X				X	
2	X	X	X					X
2.5	X	X	X					
3	X	X	X					

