Laboratory values outside the reference limit suspected to be of any clinical significance will be repeated. Volunteers in whom suspected clinical significance is confirmed will either not be included or if already enrolled will be followed until normalisation or for as long as the Investigator considers necessary. Additional laboratory variables may be performed for safety reasons if judged appropriate by the Investigator. Further details are provided in the Laboratory Manual.

The safety laboratory samples will be analysed using routine methods at

NB. In case a healthy volunteer shows an AST or ALT ≥ 3 x ULN or total bilirubin ≥ 2 x ULN please refer to [Appendix D](#) 'Actions required in cases of combined increase of Aminotransferase and Total Bilirubin – Hy's Law', for further instructions.

For blood volume see Section [7.1](#).

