6.4.10 Ophthalmology

A full ophthalmologic examination including a slit-lamp funduscopy, best corrected visual acuity, and intraocular pressure measurement must be performed at screening for all volunteers. If a volunteer experiences visual disturbance the ophthalmological algorithm should be followed for diagnosis and management of these symptoms. Volunteers should undergo an ophthalmological examination and Optical Coherence Tomography scans should be considered.

The same ophthalmic expert will perform ophthalmic assessments on each occasion where possible.

During the study the healthy volunteers will be asked to report if they experience any eye symptoms such as dry eyes, grittiness, or irritation. In case of clinically relevant ophthalmological abnormalities, an additional full examination will be performed.

Any corneal changes must be monitored frequently, with therapeutic intervention as appropriate until resolution. Any abnormalities elicited will be recorded as an AE.

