4.2 Potential Hy's Law Criteria met

If the healthy volunteer does meet PHL criteria the Investigator will:

- Determine whether PHL criteria were met at any study visit prior to starting study treatment in the presence of liver metastases (See Section 6)
- Notify the AstraZeneca representative who will then inform the central Study Team

The Study Physician contacts the Investigator, to provide guidance, discuss and agree an approach for the study healthy volunteers' follow-up and the continuous review of data. Subsequent to this contact the Investigator will:

- Monitor the healthy volunteer until liver biochemistry parameters and appropriate clinical symptoms and signs return to normal or baseline levels, or as long as medically indicated
- Investigate the etiology of the event and perform diagnostic investigations as discussed with the Study Physician
- Complete the three liver paper CRF Modules as information becomes available
- If at any time (in consultation with the Study Physician) the PHL case meets serious criteria, report it as an SAE using standard reporting procedures

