5. REVIEW AND ASSESSMENT OF POTENTIAL HY'S LAW CASES

The instructions in this Section should be followed for all cases where PHL criteria were met.

No later than 3 weeks after the biochemistry abnormality was initially detected, the Study Physician contacts the Investigator in order to review available data and agree on whether there is an alternative explanation for meeting PHL criteria other than DILI caused by the IMP. The AstraZeneca Medical Science Director and Global Safety Physician will also be involved in this review together with other subject matter experts as appropriate.

According to the outcome of the review and assessment, the Investigator will follow the instructions below.

If there **is** an agreed alternative explanation for the ALT or AST and TBL elevations, a determination of whether the alternative explanation is an AE will be made and subsequently whether the AE meets the criteria for a SAE:

- If the alternative explanation is **not** an AE, record the alternative explanation on the appropriate CRF

- If the alternative explanation is an AE/SAE, record the AE /SAE in the CRF accordingly and follow the AZ standard processes

If it is agreed that there is **no** explanation that would explain the ALT or AST and TBL elevations other than the IMP:

- Report an SAE (report term ‘Hy’s Law’) according to AstraZeneca standard processes.
 - The ‘Medically Important’ serious criterion should be used if no other serious criteria apply
 - As there is no alternative explanation for the HL case, a causality assessment of ‘related’ should be assigned.

If, there is an unavoidable delay, of over 3 weeks, in obtaining the information necessary to assess whether or not the case meets the criteria for HL, then it is assumed that there is no alternative explanation until such time as an informed decision can be made:

- Report an SAE (report term ‘Potential Hy’s Law’) applying serious criteria and causality assessment as per above
- Continue follow-up and review according to agreed plan. Once the necessary supplementary information is obtained, repeat the review and assessment to determine whether HL criteria are met. Update the SAE report according to the outcome of the review

6. ACTIONS REQUIRED WHEN POTENTIAL HY’S LAW CRITERIA ARE MET BEFORE AND AFTER STARTING STUDY TREATMENT

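### The protocol ends monitoring of unresolved AEs and SAEs at an optional phone call, while its corneal and liver rules require monitoring beyond it and nothing says which rule prevails

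*Protocol*

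**What the plan says.** Section 6.4.3 makes follow-up of unresolved AEs an investigator duty and then names one means for it: "A follow-up phone call can be conducted 5 to 10 days following discharge". It closes with: "Adverse events will not be monitored following the follow-up phone call". Footnote l to Table 2 has the same ending with serious events named: "Unresolved AEs/SAEs will not be monitored following the follow-up phone call". Section 6.4.1 would bring serious events under the Section 6.4.3 sentence in any case: "The term AE is used to include both serious and non-serious AEs".

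Three other places tie the end of follow-up to outcome or medical judgement:

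- Section 6.4.10, eye findings: "Any corneal changes must be monitored frequently, with therapeutic intervention as appropriate until resolution". The same paragraph has abnormalities recorded as AEs.
- Appendix D, Section 4.2, potential Hy's Law cases: "Monitor the healthy volunteer until liver biochemistry parameters and appropriate clinical symptoms and signs return to normal or baseline levels". The sentence goes on to allow, as an alternative, monitoring for as long as is medically indicated.
- Section 6.4.5, laboratory values of confirmed clinical significance: volunteers "if already enrolled will be followed until normalisation or for as long as the Investigator considers necessary".

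Appendix D, Section 5 sets the joint sponsor and investigator review of a liver case at "No later than 3 weeks after the biochemistry abnormality was initially detected". If the necessary information is delayed beyond that, the case is reported as an SAE and follow-up continues to an agreed plan with no end date.

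**The concern.** A categorical end to monitoring stands beside duties that have no fixed end, and the same event can fall under both. Site staff who work from the study plan table would see footnote l, which names SAEs and points to no exception.

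The events affected are ones the protocol anticipates. Section 1.3.1 lists transaminase increases and blurred vision among the events relevant to healthy volunteers. Section 1.1 reports tissue mineralisation, including in the cornea, as the exception to the reversibility of most nonclinical changes. Table 2 places post-dose safety chemistry and haematology at Day 7 only. (Table 6 budgets four samples of each against three scheduled visits and gives the fourth no time.) A post-dose laboratory signal may thus first appear at discharge, just as the 5 to 10 day window opens.

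At stake are the safety of volunteers who expect no benefit from the drug, and the completeness of outcome data for the safety and tolerability objective.

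**Working it through.** The plan gives no figure to reproduce. The check sets the rules side by side and then counts days.

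**Which rule covers which event**

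| Event | End under 6.4.3 / footnote l | End under the specific section | Do both rules cover it? |
|---|---|---|---|
| Corneal change | The call | Resolution (6.4.10), no alternative stated | Yes: 6.4.10 makes it an AE |
| Potential Hy's Law case | The call, once it is an AE or SAE | Normal or baseline, or as long as medically indicated (App. D 4.2); continues past 3 weeks if information is late (App. D 5) | Yes, for a case that is an SAE |
| Clinically significant laboratory value | The call, if it is an AE or SAE | Normalisation, or the investigator's judgement (6.4.5) | Only in part |

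The third row is partial because Section 6.4.3 itself says that deterioration in a protocol-mandated laboratory value is reported as an AE only if it meets a seriousness criterion. Non-mandated parameters count when the change is clinically relevant. An asymptomatic, non-serious change in a mandated value is not an AE, so the end-of-monitoring sentence does not reach it and Section 6.4.5 governs alone.

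**Does any text rank the rules?** Section 6.4.3 refers readers to Appendix D when AST or ALT is at least 3 times, or bilirubin at least 2 times, the upper limit of normal. It does not say that Appendix D overrides the end of monitoring. Sections 6.4.5 and 6.4.10 and Appendix D do not say so either, and footnote l mentions none of them.

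**Day count, discharge on Day 7**

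- Call window: 7 + 5 = Day 12 to 7 + 10 = Day 17.
- Outer limit of the liver review for an abnormality first detected on Day 7: 7 + 21 = Day 28.
- Difference: 28 − 17 = 11 days to 28 − 12 = 16 days.

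A case still lacking information after Day 28 becomes an SAE with continuing follow-up, although by then the call window has closed and footnote l says unresolved SAEs are not monitored.

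**If the call is not made.** The call is permitted, not required. Monitoring is said to stop after it. With no call, the text gives no end point.

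**The case against.** The strongest reply is that Section 6.4.3 is a general rule and the others are specific procedures that naturally prevail. The liver case is signposted from within Section 6.4.3, and again in 6.4.5. Section 6.4.3 also obliges the investigator to follow unresolved AEs and lets the sponsor request information on events ongoing at study end. On this reading a sensible site would keep monitoring.

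Part of this stands. The follow-up duty and the sponsor's right make it less likely that an event is dropped, so the risk is a possibility only. But the right to ask for information is not a duty to monitor, and the cross-reference to Appendix D ranks nothing. No such cross-reference exists for the cornea.

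The eye rule could also be read so that its end point attaches to treatment rather than monitoring. The sentence does not force that reading, and the uncertainty is itself a reason to clarify.

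Two stronger readings are tempting and are not supported:

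- A reader might infer that all three sections demand follow-up to full recovery, so that a site can never comply with both rules. Sections 6.4.5 and Appendix D 4.2 each allow a discretionary end, and most mandated laboratory changes are not AEs.
- A reader might take the 11 to 16 days as monitoring lost. Day 28 is the latest date for a review of available data, which may happen sooner. It is not a monitoring end point.

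**Conclusion.** The contradiction is real. It is direct for corneal changes and for potential Hy's Law cases that are SAEs. It is limited for Section 6.4.5, where it reaches only laboratory changes that qualify as AEs or SAEs. No passage says which rule prevails, and the end of monitoring is undefined if the call is not made.

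The day count shows only that the protocol's own liver procedure can run 11 to 16 days past the call. It assumes discharge on Day 7, first detection on that day, and a case meeting both the transaminase and bilirubin criteria. An earlier or extended residency would move the dates. With six volunteers and a single dose, few if any are likely to be affected, but the text matters for any who are.

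**What to change.** Reconcile the passages. In Section 6.4.3 and Table 2 footnote l, state how the end-of-monitoring sentence relates to Sections 6.4.5 and 6.4.10 and to Appendix D, so that each type of event has one identifiable rule for the end of follow-up. State also what ends monitoring when the optional call is not made. Which rule should apply to which event is a clinical decision for the sponsor and investigator.

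The cost is wording in two places. No scheduled visit or sample is added, and the outcome-based follow-up is already in other sections.
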